There has been no additional adaptation of the Kitbag itself from the school setting but the support is tailored to the social work setting, focusing on the relationship-based and reflective practice skills of the social workers and their role in leading the shift in practice within their teams.

As mentioned above, we expect that the version of the programme trialled will involve considerably more use of the Kitbag Online than in non-Covid-19 times. We attempt to address the generalisability of the findings in the implementation and process evaluation (please see below).

Logic model

* indicates outcomes that will be measured.

Impact Evaluation

Research questions

Primary research questions

Child outcomes:

- Primary outcome 1: What is the impact of the “Putting the Kitbags to work” programme on the number of **escalations and de-escalations** of eligible children supported by social workers? The comparison is between eligible children supported by social workers in teams randomly allocated to the intervention arm compared with eligible children supported by social workers in teams randomly allocated to the control arm within the intervention period.
- Secondary outcome 1: What is the impact of the “Putting the Kitbags to work” programme on the **behaviour** of eligible children supported by social workers? The comparison is between eligible children supported by social workers in teams randomly allocated to the intervention arm compared with eligible children supported by social workers in teams randomly allocated to the control arm. The outcome will be measured by the total difficulties score of the Strengths and Difficulties Questionnaire. The population will be restricted to children who’ve been looked after continuously for 12 months or more whose SDQ has been assessed from T4 - T12.

Social worker outcomes:

[figure not shown]
- Secondary outcome 2: What is the impact of the “Putting the Kitbags to work” programme on the **self-efficacy** (as measured by the competency subscale of the Work-Related Basic Needs Satisfaction scale) of social workers and family support workers in teams randomly allocated to the intervention arm compared with social workers and family support workers in teams randomly allocated to the control arm? The outcome will be measured at month 6 and month 13 after intervention began.

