Social workers and family support workers in eligible teams are eligible to receive Kitbags. Family support workers who work in the eligible statutory teams are eligible to be part of our

sample as they do a considerable amount of the direct work with the children and young people. We consider team managers as not eligible because they are unlikely to do much direct work with children and young people. Social workers and family support workers who have permanent contracts are given the Kitbags to keep, and so if they leave the local authority's employment, a new Kitbag will need to be given to their replacement. (Agency workers leave at a sufficiently high rate that they will be asked to leave the Kitbag with their team for their replacement if they leave). We also allow for 15% contingency to account for these circumstances. If social workers or family support workers change teams within the local authority, they are asked to adopt the treatment assignment of their new team to prevent contamination but for analysis purposes they will be considered according to their original team treatment allocation.

Foster carers and kinship carers

Additionally, local authority foster carers and kinship carers who care for children supported by social workers and family support workers in treated teams will receive a Kitbag. Foster carers who care for children supported by social workers and family support workers in treated teams and employed by independent fostering agencies or other local authorities are not eligible to receive a Kitbag. This is to concentrate the resources with the participating local authorities. By kinship carers, we mean carers of children who are looked after on a voluntary, interim or full care order whose placement type is a placement with a relative or friend. The children supported by social workers and family support workers in treated teams will still have the opportunity to benefit from the Kitbag through their social worker or family support worker.

Local authorities may recruit new foster carers and kinship carers may start their caring responsibilities over the intervention period, and these foster carers and kinship carers who are caring for children supported by a social worker in a treated team will be given a Kitbag. We also allow for 15% contingency to account for these circumstances.

Table 2: Number of Kitbags for each local authority

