If the sample is imbalanced with respect to team type (CIN / CP, CLA, children with disabilities) within the local authority, we will re-randomise (setting a new seed). We take imbalance to be the proportion of teams of that type within the local authority assigned to the intervention to be greater than 0.75 or less than 0.25 (i.e. $\frac{3}{4}$ or $\frac{1}{4}$ teams) except where there is only one team of that type in the local authority.

We will also report the mean proportion of social workers to family support workers, and the mean proportion of permanent staff to agency staff, by treatment allocation but will not re-randomise if there is imbalance in treatment allocation on these variables. With a relatively small number of teams to allocate, we have decided to prioritise team type (within the local authority) to enable us to compare the impact of the programme on these subgroups.

Data collection

We have several data collection methods:

Impact evaluation

- Children and young people:
 - administrative data to measure children's social care involvement
- Social workers:
 - online survey to measure self-efficacy, stress
 - administrative data to measure sickness absence
- Foster/kinship carers:
 - online survey to measure self-efficacy

⁷ Due to a delay of the required data from Oxfordshire County Council, the randomisation was conducted for the three other local authorities first, and the teams from Oxfordshire County Council were allocated separately.

Sample size / MDES calculations

		MDES (Proportion of a Standard Deviation)
MDES		0.127
Proportion of variance in child's outcome explained by:	Child covariates (including baseline measure)	0.8
	Social Worker team covariates	0.1 (3 covariates)
Intraclass correlations (ICCs)	Team	0.03
Alpha		0.05
Power		0.8
One-sided or two-sided?		Two-sided
Level of intervention clustering		Social worker team
Average cluster size		150 children in each team
Sample Size (children)	Intervention	4500
	Control	4500
	Total	9000
Sample Size (teams)	Intervention	30 (15 per local authority)
	Control	30 (15 per local authority)
	Total	60

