- for social workers and family support workers: the social worker or family support worker was a member of a team assigned to the intervention at point of randomisation and 0 else;
- for foster / kinship carers: the carer cares for a child or young person whose case is held at the point the foster carer enters the sample, by a social worker who is a member of a team assigned to the intervention at point of randomisation and 0 otherwise.

Although there is some turnover of social workers, family support workers and foster carers, about 80% of those at T0 (April 2021) will still be working with the local authority at T13 (May 2022), and so 80% will have received the full 12 months of the intervention. Binarising the treatment seems a reasonable proxy in this case.

For the outcomes relating to children, treatment is coded as a binary variable. When children enter the sample, at either the point of randomisation, or the point they become eligible (e.g. their case opens and meets other criteria) they will be allocated to treatment if the team of their allocated social worker was randomised to treatment.

Covariates

Including control variables increases the precision of the estimate. In each regression, we control for a number of relevant covariates. We outline different categories of covariates below.

Site effects

We include site fixed effects but not site-treatment interaction terms.

Previous outcome measures

We control for the previous measurements of the outcome variable where data is available. For the survey-based measures for social workers, family support workers and foster carers, the same measures will be asked at T6 (October 2021) and T13 (May 2022), and for administrative data we expect previous values to be available. For the outcomes of the CYP and parents / carers (including kinship carers), the previous measure of the outcome will be at T0 (April 2021) or when they entered services if they entered services after T0 (April 2021).

Other covariates

For CYP outcomes (primary outcome i) and secondary outcome i)), we include the following vector of individual-level covariates:

- gender (coded as male, female, or other/missing)
- age group (4-11, 12-17, 18 years, or missing with 4-11 as the reference category)
- ethnicity (Asian / Asian British, Black / African / Caribbean / Black British, Mixed / Multiple ethnic groups, Other ethnic group, White, missing; with the majority group as the reference category)

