- disability status (Yes, No, Don't know/missing with No as the reference category)
- most recent type of CSC intervention (coded as :
 - Child in Need
 - Child Protection Plan
 - Looked After - LA fostering / kinship care
 - Looked After - IFA / other LA fostering other placement type
 - missing;
 - with Child in Need as the reference category)

- unaccompanied asylum seeking child (yes, no, or missing with no as the reference category)
- if possible, whether their social worker has changed over the intervention period (yes, no, missing with no as the reference category)
- for the primary outcome 1-3 only, the number of status changes within the intervention period (numeric: as per the children's social care interaction outcome variable)

For social worker and family support worker outcomes, we include the following individual-level covariates:

- gender (coded as male, female, or other/missing),
- role (social worker, family support worker, or missing; with social worker as the reference category)
- contract type (permanent, agency or missing; with permanent as the reference category)
- the number of years experience (Associated and Supported Year in Employment / years<1, 1≤ years<4, 4≤years<9, 9years<15, ≥15 with ASYE as the reference category)

We include the following team-level characteristics (measured at T0):

- team type as categorised in Table 1 above (CINP / CPP, CLA, children with disabilities with CINP / CPP as the reference category)
- team size (numeric)
- percentage social worker or family support worker (numeric)
- percentage permanent or agency workers (numeric)

For foster carers (where we can match the data):

- gender (coded as male, female or other/missing)
- employer (LA foster carer, employed by an independent fostering agency or another local authority, or missing; with LA foster carer as the reference category)
- number of years experience (numeric)

Where the foster carer answering the survey is different between pre and post intervention data collection (e.g. the foster carer who answered at baseline isn't available or no longer fosters the child), the post data will be collected from the available foster carer and their pre data will be recorded as missing. The data collected from the foster carer who answered at the pre data collection point will be discarded (we won't impute their outcome data).

Please see the regression specification.

Standard errors

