
local authorities, after implementation of Kitbag?
 
B). What is the range and diversity in use of Kitbag with different subgroups and team types?
 
Implementation RQ2:
 
A). How are staff supported to use Kitbags in practice?
	
 ● Self-reported resources staff use (in both intervention and comparator groups) in their direct work with families including how they fund and access them ● How direct work is recorded and discussed between social worker and team manager ● The average reported frequency of use of Kitbag ● Whether there is any difference in use of Kitbag depending on the team type ● Whether use of Kitbag differs depending on factors such as: disability or additional needs, age, and level of need of the child ● Frequency of use of Kitbag at team meetings ● How staff describe use of Kitbag with different subgroups e.g. across age, disability, level of need of the child, and also at their own team level ● Staff satisfaction with how the programme was implemented (e.g. distribution of Kitbags, workshops, support from Kitbag leads, replacing materials as needed) ● Average proportion of Kitbag leads attending the monthly workshops (The number of Kitbag lead attendees divided by 	
Survey questions (multiple choice and free-text) at T6-T13 with both intervention and comparator groups
 
Additional questions on recording use of Kitbag will be asked for those in the intervention group and a review of Kitbag recording sheets will also take place
 
Survey at T6-T13 with the intervention group
 
Focus group discussions at T10-T12 with the intervention group only
 
Survey with intervention group at T6-T13
 
Admin data collected by UoS / IFF at T13

---	---	---

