
B). What are the contextual facilitators and barriers to implementation?
	
the number of Kitbag leads, averaged across all workshops)
 
 ● The proportion of social workers and family support workers in intervention teams who agree that information from the monthly workshops is being disseminated well ● How staff describe the information disseminated around using Kitbag and whether staff can identify any improvements ● How staff describe what prevents or supports them to use Kitbag and whether they can identify any other contextual factors ● How staff describe what prevents or supports them to use Kitbag and whether they can identify any other contextual factors ● Whether there is any sustainability planning around use of Kitbag (i.e. cost of replacing items, on-going training needs etc.) 	
Survey with intervention group at T6-T13
 
Focus group discussions at T10-T12 with the intervention group only
 
Focus group discussions at T10-T12 with the intervention group only
 
Survey with the intervention and comparator group at both T6-T13
 
Focus group discussions at T10-T12 with the intervention group only
 
Focus group discussions at T10-T12 with Kitbag super leads and Kitbag leads in the intervention group only

Acceptability and adaptation
 
RQ3). What do practitioners (social workers, family support workers and foster carers) who receive a Kitbag and children who work with a Kitbag think of
	
 ● How practitioners who've received a Kitbag describe the intervention Kitbag and whether they think any changes are needed to content or delivery ● How children who've worked with a Kitbag 	
Focus group discussions with social workers and family support workers and interviews with foster carers at T10-T12
 
Interviews with children at T10-T12 with the intervention group only

Kitbag and would they make any changes to the content or how the direct work is completed?
	
describe the intervention Kitbag and whether they think any changes are needed to content or delivery
	

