The interviews with foster carers will be semi-structured, via telephone or a virtual platform, and will last up to half an hour. Participants will be given the choice of platform between Zoom, Microsoft Teams and a phone call. Prior to the interview an information sheet will be shared with participants and the researcher will discuss the evaluation and measures taken to ensure confidentiality and privacy. The participant will have the chance to ask any questions and will be asked whether they consent to the interview being audio-recorded. If consent to record the call is not given, descriptive notes will be written by the researcher and written up following the call.

Interviews will be recorded, with consent, transcribed and pseudonymised prior to analysis.

Survey

A survey, asking different questions at different timepoints, will be shared with social workers and family support workers (including Kitbag Leads and team managers) from the eligible teams at T6 and T10-T13. The plan in v1 of the protocol was to send social workers and family support workers the survey at T1 instead of T6. The survey was delayed to allow social workers and family support workers to prioritise collecting the consents from the individual with parental responsibility and to avoid the confusion of too many forms.

The survey will help us to answer all four research questions and in particular we seek to understand:

- Confidence with using Kitbag
- How often social workers complete direct work with children and families
- The kinds of activities completed and the resources used for direct work
- How staff are supported to complete direct work with children and families
- How staff record direct work
- Whether staff feel supported to use Kitbag and how they are supported
- Frequency of use of Kitbag including whether some components are used more often than others
- Frequency of use of the Kitbag within the social worker team
- Support from team manager in supervision to use Kitbag

A survey will also be sent to foster and kinship carers in the intervention group at T6 and T10-T13. This will assess use of Kitbag and the outcome measure of self-efficacy.

Observation of workshops

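### Kitbag Leads are counted among the staff who rate the dissemination and support that the Leads themselves provide, and the place of team managers in the staff survey is left unclear

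*Protocol*

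**What the plan says.** **The survey.** In the Protocol's implementation and process evaluation, the Survey section sends the staff questionnaire to "social workers and family support workers (including Kitbag Leads and team managers) from the eligible teams at T6 and T10-T13". According to the Data collection schedule, Leads are surveyed within the social worker and family support worker group, but team managers are listed as a group of their own. Only the foster carer version is said to be adapted.

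**The indicators.** For RQ2, the Design and Methods table takes intervention-team social workers and family support workers as a denominator and counts the share of them found to "agree that information from the monthly workshops is being disseminated well". A further indicator is how satisfied staff are with implementation, with examples that include "support from Kitbag leads, replacing materials as needed". Neither indicator excludes Leads, and no reporting by role is stated.

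**The Leads.** The section on the intervention (What) appoints two Leads in each intervention team. They attend monthly workshops and then support their colleagues. In some local authorities one of the two is a team manager or senior practitioner.

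**The managers.** The Participants section states: "We consider team managers as not eligible because they are unlikely to do much direct work with children and young people". Self-efficacy and stress (secondary outcomes 2 and 3) come from the staff survey, listed under Data collection as "online survey to measure self-efficacy, stress". Their comparison is one "of social workers and family support workers in teams randomly allocated to the intervention arm compared with social workers and family support workers" outside it. Coding of treatment as 1 requires that "the social worker or family support worker was a member of a team assigned to the intervention at point of randomisation and 0 else". Among the covariates is "role (social worker, family support worker, or missing; with social worker as the reference category".

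**The concern.** RQ2 asks how practitioners are supported to use Kitbag. The natural reading of the two indicators is that they report the experience of staff who receive the support. As specified, they mix those staff with the people who provide it. A Lead who is asked whether workshop content is passed on well, or how good the Leads' support is, is rating their own work. If Leads answer more favourably than their colleagues, the published figure overstates the support that ordinary staff received.

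The second issue is one of wording. The Survey section places team managers inside the group for which secondary outcomes 2 and 3 are defined, while the Participants section makes them ineligible and the schedule lists them apart. No sentence says whether their answers are left out of those two outcomes. That leaves a choice about the analysed group to be made after the data are in.

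**Working it through.** The Protocol states no figure for this point, so there is none to reproduce.

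**Inputs from the Protocol**
- Intervention-arm social workers and family support workers (Table 2): 33 + 28 + 120 + 119 = 300.
- Intervention teams (sample size table): 30, so 300 / 30 = 10 staff per team.
- Team size in the Design table: 6 to 8 social workers.
- Leads: 2 per intervention team, so 30 × 2 = 60.
- Assumed survey response (Data collection schedule): 10%.

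**Assumptions, not in the Protocol**
- All Leads are social workers or family support workers.
- Leads and others respond at the same rate.
- 90% of Leads and 50% of other staff agree.
- For the manager calculation: one manager per team, equal response, and no effect of Kitbag in managers.

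**Share of Leads.** With s staff per team the share is L = 2 / s.
- s = 10: 2/10 = 20% (the same as 60/300)
- s = 8: 2/8 = 25%
- s = 6: 2/6 = 33%

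The 20% counts both staff roles. The 25% and 33% treat 6 to 8 social workers as the whole team, so they form the upper end.

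**Reported agreement.** Pooled figure = 0.5 × (1 − L) + 0.9 × L.
- s = 10: 0.5 × 0.80 + 0.9 × 0.20 = 58%
- s = 8: 0.5 × 0.75 + 0.9 × 0.25 = 60%
- s = 6: 0.5 × 0.667 + 0.9 × 0.333 = 63%

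The overstatement is L × (0.9 − agreement among others), here 8 to 13 points. With Leads still at 90%:
- if 40% of others agree, the pooled figure is 50% to 57%;
- if 60% of others agree, it is 66% to 70%.

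If one Lead in every team were a manager outside the denominator, L would halve to 1/10 to 1/6. The overstatement at 50% would then be 0.4 × 0.10 = 4 points to 0.4 × 0.167 = 7 points.

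**Managers, if they were included in secondary outcomes 2 and 3.** Their share is 1 / (s + 1), and the effect is multiplied by s / (s + 1).
- s = 10: share 9.1%, multiplier 0.91
- s = 8: share 11.1%, multiplier 0.89
- s = 6: share 14.3%, multiplier 0.86

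An illustrative effect of 0.30 SD would be estimated as 0.27 (s = 10) to 0.26 (s = 6).

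**The case against.** **The figures are descriptive.** Survey results are triangulated with qualitative findings, RQ2 also draws on focus groups, observations and workshop attendance records, and no decision rule hangs on these percentages. Reporting by role could be left to later detail. This stands as a limit on the consequence. It does not remove the problem, because the dissemination indicator's denominator is fixed in the Protocol and takes in the Leads.

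**Leads may be fewer.** Some are managers, and the dissemination indicator does not name managers. That is fair, and it lowers the Lead share as shown above.

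**Stronger readings that the documents do not support**
- *Managers dilute self-efficacy and stress.* A reader might infer this from the Survey section, and might add that a manager's role would be coded as missing and the return kept. But being sent a survey is not being in the outcome analysis. The research questions, treatment coding and role covariate name only social workers and family support workers, the schedule lists managers separately, and nothing assigns them to the missing level. Nor is zero benefit in managers established, since Kitbag is also meant for team meetings and some managers are Leads.
- *Managers could make up a quarter or a third of respondents.* This needs managers to reply several times as often as staff. The Protocol gives no response rate by role.
- *Leads could dominate the figures.* At 10% response about 30 intervention staff reply. Making 18 of them Leads would give 60% Leads and a figure of 74%, but it leaves only 12 replies from the other 240 staff. That is 5%, half the rate the Protocol assumes.
- *Leads should leave the outcome comparison too.* They should not. Leads who are social workers or family support workers belong in it under intention to treat.

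**Conclusion.** The point about Leads holds on the stated text. Followed as written, the plan lets about 20% to 33% of the denominator rate dissemination and support that they themselves provide, if all Leads are social workers or family support workers. Under the assumed agreement rates and equal response, ordinary staff at 50% would be reported as 58% to 63%. The direction depends on Leads being the more favourable group, which is plausible but not documented.

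The point about managers is an ambiguity to close, not a stated pooling. If it were resolved the wrong way, the attenuation would be about 9% to 14% under the three manager assumptions. Managers would be present in both arms, so this would pull the effect towards zero and would not manufacture a benefit.

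Neither part touches the primary outcome.

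**What to change.** 1. Record role in the staff survey: ordinary staff, Kitbag Lead, team manager.
2. Calculate the dissemination and Lead-support indicators among intervention staff who are neither Leads nor managers, and show Leads and managers separately.
3. Reconcile the Survey section with the Participants section and the schedule. State that secondary outcomes 2 and 3 use only staff eligible under the Participants section, in both arms, and that Leads who are social workers or family support workers stay in under intention to treat. Managers' answers remain available to the process evaluation.

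The cost is one survey item and a few sentences. The downside is fewer respondents per figure: of about 30 intervention replies at 10% response, 24 would remain if Leads are 20% of them (30 × 0.80), and 20 if they are a third (30 × 2/3).

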- Secondary outcome 3: What is the impact of the “Putting the Kitbags to work” programme on the **stress** (as measured by the “Stress in General” scale) of social workers and family support workers in teams randomly allocated to the intervention arm compared with social workers and family support workers in teams randomly allocated to the control arm? The outcome will be measured at month 6 and month 13 after intervention began.
- Secondary outcome 4: What is the impact of the “Putting the Kitbags to work” programme on the **number of sick days** taken by social workers and family support workers in teams randomly allocated to the intervention arm compared with social workers and family support workers in teams randomly allocated to the control arm from T1 to T13?

Foster carer outcomes:

- Secondary outcome 5: What is the impact of the “Putting the Kitbags to work” programme on the **self-efficacy** of foster and kinship carers supported by social worker teams randomly allocated to the intervention arm compared with foster carers supported by social worker teams randomly allocated to the control arm as measured? The outcome will be measured at month 6 and month 13 after intervention began. The population will be restricted to local authority employed foster carers only..

Design

Trial type and number of arms	Parallel multi-site cluster RCT (2 arms)
Unit of randomisation	Social Work Team (6-8 social workers)
Stratification variables (if applicable)	Local authority and team type (CIN+CP/CLA/Children with disabilities)

Participants

Oxfordshire County Council, the London Borough of Bexley, Haringey Council and Warwickshire County Council shall be participating in the trial.

Teams

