Focus groups	T10-T12	
We will send information about the focus groups to the practitioners via the Kitbag super lead and then purposively sample aiming for a heterogenous sample of practitioners from different team types and of different roles.
 
For the focus group discussions for the super leads, all will be invited to attend.

Interviews (n=16)	T10-T12	
Children: Practitioners who attend the focus group discussion will be asked to identify children on their caseload who may be open to participating.
 
Foster carers: the Kitbag leads in the fostering teams will be asked to send information about the interviews to the foster carers. We

		will purposively sample aiming for a heterogenous sample of foster carers of children of different ages.
Survey (assume 10% response rate)	T1 T13	A survey will be shared with all staff (i.e. no sampling) across intervention and comparator teams: 
 • Social workers and family support workers (includes Kitbag Leads) • Inhouse foster carers (the survey will be adapted slightly for this group) • Team Managers
Observations of workshops (n=4)	T3-T4	A researcher or research assistant will observe at least one workshop per local authority.

Analysis

Qualitative data preparation and analysis of interview and observational data

Interviews will be recorded, transcribed and pseudonymised prior to analysis. Qualitative analysis of interview and observational data will use NVivo software and follow a thematic analysis approach. This will involve data familiarisation, checking accuracy of transcription, labelling the data with descriptive codes and developing themes which describe patterns across the data to answer the pre-specified research questions. Analysis will look for patterns, consistencies and inconsistencies across different informants and time points that might be informative for the research questions.

The following steps will be taken to ensure rigor in the analysis and reporting of qualitative data:

- Confidence that the findings are an accurate reflection of participant experience will be ensured through presentation of examples of participant responses using quotes, and triangulation between different informants and data collection methods.
- The degree to which findings are transferable to other contexts will be considered through detailed description of contextual factors, and collection of data from a range of informants to gather a range of perspectives.

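### The protocol contradicts itself on whether control-arm carers receive the survey that measures carer self-efficacy (secondary outcome 5)

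*Protocol*

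**What the plan says.** Under Implementation and process evaluation, Methods, Survey, the carer survey is described in two sentences: "A survey will also be sent to foster and kinship carers in the intervention group at T6 and T10-T13", and "This will assess use of Kitbag and the outcome measure of self-efficacy". The staff survey in the same subsection goes to the eligible teams with no limit by arm.

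Under Research questions, secondary outcome 5 sets the self-efficacy of foster and kinship carers linked to intervention teams against that of controls: "compared with foster carers supported by social worker teams randomly allocated to the control arm as measured". It continues: "The outcome will be measured at month 6 and month 13 after intervention began. The population will be restricted to local authority employed foster carers".

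Under Independent variable of interest: treatment, a carer is coded 1 if the child's social worker is "a member of a team assigned to the intervention at point of randomisation and 0 otherwise".

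The Survey row of the Data collection schedule says: "A survey will be shared with all staff (i.e. no sampling) across intervention and comparator teams". In-house foster carers are one of the groups listed beneath. The time points in that row are T1 and T13.

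**The concern.** The carer survey is not a process-only questionnaire, because the protocol names it as the vehicle for an outcome of the impact evaluation. The Version note says that outcomes are now limited to administrative data and online surveys, so this survey is the only source for carer self-efficacy. A fieldworker who reads the Survey subsection sees staff in all eligible teams surveyed, followed by carers in one arm only, and could reasonably act on that.

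At stake is the whole of secondary outcome 5. Carer self-efficacy is a hypothesised mechanism in the logic model and one of the secondary outcomes to which the Hochberg adjustment applies. Control responses not collected in their window cannot be recovered later.

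**Working it through.** No power or sample size figure is given for the carer outcome, so there is none to reproduce. The check is a comparison of the relevant places, followed by the consequence for the model.

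**1. Who receives the carer self-efficacy items?**

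| Place in the protocol | Arms | Carers named | Timing |
|---|---|---|---|
| Research questions, secondary outcome 5 | both | foster and kinship on the intervention side, foster only on the control side, then local authority employed foster carers only | months 6 and 13 |
| Data collection (impact evaluation) | no limit by arm | foster and kinship | none given |
| Outcome measures, 2v | not stated | local authority employed foster carers only | none given |
| Treatment variable | both (1 or 0) | foster and kinship | not applicable |
| Covariates, previous outcome measures | not stated | foster carers for the survey measures; carers including kinship for the previous measure | T6 and T13 for the survey measures; T0 or entry to services for the previous measure |
| Process evaluation, Survey | **intervention only** | foster and kinship | T6 and T10-T13 |
| Data collection schedule | both | in-house foster carers | T1 and T13 |

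The Survey subsection is the only place that limits the self-efficacy measure to one arm. The places also differ on carer type and on timing.

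**2. Can the schedule row settle it?** Not on its own. The Survey subsection explains that the staff survey was planned for T1 in version 1 and has moved to T6. The schedule row still shows T1, so at least part of it is superseded, while the Survey subsection carries the revised timing. The row also omits kinship carers.

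**3. What happens if the Survey sentence is followed literally?** The model for carer outcomes in Regression specification is

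Y = β0 + β1·D + (local authority, previous outcome, individual and team terms) + error.

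With intervention carers only, D = 1 for every record. The column for D then equals the intercept column, so only β0 + β1 is identified and β1 has no estimate. A before-after comparison within the intervention arm is no substitute. Kitbags are distributed in May 2021 and the first survey is at T6 (October 2021), so the surveys give no pre-exposure score for carers already in post.

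**4. Is there other evidence of intent?** Table 2 counts intervention-group carers, kinship carers included: 57 + 100 + 119 + 148 = 424. Adding the hold-back of 43 for new carers gives 467. The Data protection section expects data on about 1000 foster carers, which fits two arms better than one. Both figures are approximate and the second does not define its population, so this is supporting evidence only.

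**5. Conditional illustration of size.** At the 10% response assumed in the schedule, 0.10 × 424 ≈ 42 intervention responses, against 0 control responses under the literal reading. The 10% comes from the row that names both arms, and 424 includes kinship carers who may fall outside the analysed population. The 42 is therefore only indicative; the zero follows directly from the sentence.

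**The case against.** The strongest reply is that a single sentence in the process-evaluation methods is out of line and the rest of the protocol is sound. The research question, the treatment coding, the impact-evaluation data collection list and the schedule all presuppose two arms. Recruitment says carers are identified through the same mechanisms as staff, and staff are identified from eligible teams in general. The sentence probably runs together two contents: Kitbag use, which makes sense only in the intervention arm, and self-efficacy, which is needed in both.

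Most of that stands. A reader might infer from the Survey sentence that the trial was designed to leave secondary outcome 5 without a control arm. The documents do not support that: nothing records a decision to drop control carers, and "A survey will be shared with all staff (i.e. no sampling) across intervention and comparator teams" says the opposite.

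Nor need the loss be total. If the error were corrected after T6 but before T13, an endline comparison would remain possible. The T6 score enters only as a covariate, and the missing data strategy drops a covariate with more than 30% missing. The price would then be lost precision and lost adjustment for the earlier score.

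The reply does not make the sentence harmless. It is current text, it is the most specific statement about the carer mailing, and it carries the updated timing where the schedule row does not. Likely intent does not correct a written instruction.

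**Conclusion.** The protocol contains an internal contradiction over who receives an outcome instrument. As written, the Survey sentence is incompatible with secondary outcome 5 and with the carer treatment variable. Followed literally, it yields no control responses and no estimable treatment effect for that outcome. The contradiction itself is certain from the text. The loss of the outcome is conditional on fieldwork following that sentence at both time points. The intended design is most likely two-arm, so this should not be read as a choice to omit controls.

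The effect is confined to one secondary outcome; the primary outcome and the staff outcomes are untouched. Correction is still needed before the carer survey is fielded, because the sentence states a wrong rule and missed responses cannot be collected afterwards.

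**What to change.** Amend the Survey subsection so that the self-efficacy items go to eligible carers linked to both intervention and control teams, at both time points. Limit only the Kitbag-use items to the intervention arm.

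Then align secondary outcome 5, Outcome measures 2v, the Survey subsection and the Data collection schedule on two matters:

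- **Recipients.** State whether kinship carers belong to the analysed population, given the restriction to local authority employed foster carers, and use the same definition for both arms.
- **Timing.** Use one set of time points in place of T1, T6, T10-T13 and T13, and make the previous-measure rule under Covariates agree with it.

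No new instrument is needed. The cost is an additional online survey mailing to control-arm carers. The protocol does not give their number. If the figure of about 1000 foster carers covers both arms and is comparable with Table 2, it would be about 1000 − 424 = 576, which is an inference and not a stated count.
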